#### **10.1.8      Source documents**

All source documents must be accurate, clear, unambiguous, permanent, and capable of being audited. They should be made using some permanent form of recording (ink, typing, printing, optical disc). They should not be obscured by correction fluid or have temporary attachments (such as removable self-stick notes). Photocopies and/or printouts of eCRFs are not considered acceptable source documents.

Source documents are original records in which raw data are first recorded. These may include hospital/clinic/general practitioner records, charts, diaries, x-rays, laboratory results, printouts, pharmacy records, care records, ECG or other printouts, completed scales, quality of life questionnaires, or video, for example. Source documents should be kept in a secure, limited access area.

Source documents that are computer generated and stored electronically must be printed for review by the monitor (eg, ECG reports). Once printed, these copies should be signed and dated by the investigator and become a permanent part of the participant's source documents. The investigator will facilitate the process for enabling the monitor to compare the content of the printout and the data stored in the computer to ensure all data are consistent.

Electronic data records, such as Holter monitor records or electroencephalogram records, must be saved and stored as instructed by UCB (or designee).

#### **10.1.9      Study and Site Closure**

The sponsor designee reserves the right to close the study site or terminate the study at any time for any reason at the sole discretion of the sponsor. Study sites will be closed upon study completion. A study site is considered closed when all required documents and study supplies have been collected and a study-site closure visit has been performed.

The investigator may initiate study-site closure at any time, provided there is reasonable cause and sufficient notice is given in advance of the intended termination.

Reasons for the early closure of a study site by the sponsor or investigator may include but are not limited to:

- Failure of the investigator to comply with the protocol, the requirements of the IRB/IEC or local health authorities, the sponsor's procedures, or GCP guidelines
- Inadequate recruitment of participants by the investigator

- Discontinuation of further study medication development

#### 10.1.10 Publication Policy

The results of this study may be published or presented at scientific meetings. If this is foreseen, the investigator agrees to submit all manuscripts or abstracts to the sponsor before submission. This allows the sponsor to protect proprietary information and to provide comments.

The sponsor will comply with the requirements for publication of study results. In accordance with standard editorial and ethical practice, the sponsor will generally support publication of multicenter studies only in their entirety and not as individual site data. In this case, a coordinating investigator will be designated by mutual agreement.

Authorship will be determined by mutual agreement and in line with International Committee of Medical Journal Editors authorship requirements.

#### 10.2 Appendix 2: Clinical Laboratory Tests

- The tests detailed in the table below will be performed by the central laboratory.
- Local laboratory results are only required in the event that the central laboratory results are not available in time for either study treatment administration and/or response evaluation. If a local sample is required, it is important that the sample for central analysis is obtained at the same time. Additionally, if the local laboratory results are used to make either a study treatment decision or response evaluation, the results must be entered into the eCRF.
- Protocol-specific requirements for inclusion or exclusion of participants are detailed in Section 5.1 and Section 5.2 of the protocol.
- Additional tests may be performed at any time during the study as determined necessary by the investigator or required by local regulations.
- Laboratory/analyte results that could unblind the study will not be reported to investigative sites or other blinded personnel until the study has been unblinded, unless a safety alert requires a clinical review of the study participant.

##### Protocol-Required Safety Laboratory Assessments

Laboratory Assessments	Parameters			
Hematology	Platelet Count	RBC Indices: Mean corpuscular volume (MCV) Mean corpuscular hemoglobin (MCH) %Reticulocytes	WBC Count with Differential: Neutrophils Lymphocytes Monocytes Eosinophils Basophils	
	RBC Count			
	Hemoglobin			
	Hematocrit			
Clinical Chemistry a	Blood urea nitrogen (BUN)	Potassium	Aspartate aminotransferase (AST)/ serum glutamic-oxaloacetic transaminase (SGOT)	Total and direct bilirubin

**Protocol-Required Safety Laboratory Assessments**

Laboratory Assessments	Parameters			
	Creatinine	Sodium	Alanine aminotransferase (ALT)/ serum glutamic-pyruvic transaminase (SGPT)	Total protein b Albumin b
	Glucose (non-fasting)	Calcium	Alkaline phosphatase	
	Lactate dehydrogenase (LDH)	C-reactive protein (CRP)	Low-density lipoprotein (LDL) High-density lipoprotein (HDL) Total cholesterol Triglycerides	
Routine Urinalysis	
 
Specific gravity
 
pH, glucose, protein, blood, ketones, bilirubin, urobilinogen, nitrite, leukocyte esterase by dipstick
 
Microscopic examination (if blood or protein is abnormal)
 
			
Other Screening Tests	
 
Follicle-stimulating hormone (FSH) and estradiol (as needed in women of non-childbearing potential only)
 
Serum or urine alcohol and drug screen (to include at minimum: amphetamines, barbiturates, cocaine, opiates, cannabinoids and benzodiazepines)
 
Serum human chorionic gonadotropin pregnancy test (as needed for women of childbearing potential)
 
Serology testing (for Hepatitis A, Hepatitis B surface antigen, Hepatitis C virus antibody, and human immunodeficiency virus [HIV])
 
			
Other Tests	
The following tests are performed locally:
 
 
IGRA TB test
 
Dipstick urinalysis (including any microscopy where required)
 
Urine pregnancy dipstick testc
 
			

IGRA=interferon-gamma release assay; TB=tuberculosis.

The results of each test must be entered into the CRF.

NOTES:

a Details of liver chemistry stopping criteria and required actions and follow-up assessments after liver stopping or monitoring event are given in Section 10.6 (Appendix 6). All events of ALT  $\geq 3 \times$  upper limit of normal (ULN) and bilirubin  $\geq 2 \times$  ULN ( $>35\%$  direct bilirubin) or ALT  $\geq 3 \times$  ULN and international normalized ratio (INR)  $>1.5$ , if INR measured, may indicate severe liver injury (possible Hy's Law) and must be reported as an SAE (excluding studies of hepatic impairment or cirrhosis).

b The results of these assessments will not be reported to investigative sites or other blinded personnel until the study has been unblinded, unless a safety alert requires a clinical review of the study participant.

c Local urine testing will be standard for the protocol unless serum testing is required by local regulation or IRB/IEC.

Investigators must document their review of each laboratory safety report.

### Other protocol-required laboratory assessments

Laboratory Assessments	Parameters
Other laboratory assessments	

• LGI1 detection

• Blood sampling for PK of rozanolixizumaba

• Blood sampling for DNA and RNA analysisb

• Serum complement (████████), and plasma complement (████████)b

• Total IgGa

• IgG subclassesa

• LGI1 IgG (total and subclasses) serum quantificationa

• ██████████

• Anti-drug antibodiesa

• Optional CSF sample collectiona

• Blood sampling for exploratory biomarker analysisb

AED=antiepileptic drug; ██████████

COVID-19=coronavirus 2019; CSF=cerebrospinal fluid;

DNA=deoxyribonucleic acid; Ig=immunoglobulin; LGI1=leucine-rich glioma inactivated 1; NF-L=neurofilament light chain; PK=pharmacokinetic(s); RNA=ribonucleic acid.

a The results of these assessments will not be reported to investigative sites or other blinded personnel until the study has been unblinded, unless a safety alert prompts a clinical review of the study participant.

b The results of these assessments will not be reported to investigative sites.

### 10.3 Appendix 3: Adverse Events – Definitions and Procedures for Recording, Evaluating, Follow-up, and Reporting

Assessment and management of TB and TB risk factor as well as safety reporting requirements are provided in Section 10.12 (Appendix 12).

#### Definition of AE

AE Definition

• An AE is any untoward medical occurrence in a patient or clinical study participant, temporally associated with the use of study medication, whether or not considered related to the study medication.

• NOTE: An AE can therefore be any unfavorable and unintended sign (including an abnormal laboratory finding), symptom, or disease (new or exacerbated) temporally associated with the use of study medication.

Events Meeting the AE Definition

• Any abnormal laboratory test results (hematology, clinical chemistry, or urinalysis) or other safety assessments (eg, ECG, radiological scans, vital signs measurements), including those that worsen from baseline, considered clinically significant in the medical and scientific judgment of the investigator (ie, not related to progression of underlying disease).

- Exacerbation of a chronic or intermittent pre-existing condition including either an increase in frequency and/or intensity of the condition.
- New conditions detected or diagnosed after study medication administration even though it may have been present before the start of the study.
- Signs, symptoms, or the clinical sequelae of a suspected drug-drug interaction.
- Signs, symptoms, or the clinical sequelae of a suspected overdose of either study medication or a concomitant medication. Overdose per se will not be reported as an AE/SAE unless it is an intentional overdose taken with possible suicidal/self-harming intent. Such overdoses should be reported regardless of sequelae.
- “Lack of efficacy” or “failure of expected pharmacological action” per se will not be reported as an AE or SAE. Such instances will be captured in the efficacy assessments. However, the signs, symptoms, and/or clinical sequelae resulting from lack of efficacy will be reported as AE or SAE if they fulfil the definition of an AE or SAE.

#### **Events NOT Meeting the AE Definition**

- Any clinically significant abnormal laboratory findings or other abnormal safety assessments which are associated with the underlying disease, unless judged by the investigator to be more severe than expected for the participant's condition.
- The disease/disorder being studied or expected progression, signs, or symptoms of the disease/disorder being studied, unless more severe than expected for the study participant's condition.
- Medical or surgical procedure (eg, endoscopy, appendectomy): the condition that leads to the procedure is the AE.
- Situations in which an untoward medical occurrence did not occur (social and/or convenience admission to a hospital).
- Anticipated day-to-day fluctuations of pre-existing disease(s) or condition(s) present or detected at the start of the study that do not worsen.

#### **Definition of SAE**

If an event is not an AE per definition above, then it cannot be an SAE even if serious conditions are met (eg, hospitalization for signs/symptoms of the disease under study, death due to progression of disease).

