### 8.3.8 Anticipated serious adverse events

Serious AEs anticipated to occur in the population studied in this protocol at some frequency that is independent of drug exposure are shown in Table 8-1.

This list does not change the investigator's obligation to report all SAEs (including Anticipated SAEs) as detailed in Section 8.3.1 and Appendix 3 (Section 10.3).

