5.6.2.2 Adverse events summaries

The number and percentage of participants who experience AEs will be summarized by treatment group. The following outputs will be created:

- Incidence of TEAEs (defined as the number and percentage of participants with at least one TEAE (incidence proportion) – Overview. The following categories will be included by treatment arm:
 - Any TEAEs
 - Serious TEAEs
 - Participant discontinuation due to TEAEs (defined as TEAEs with “Did the Adverse Event Lead to Dropout ticked” as “Yes”)
 - Permanent withdrawal of IMP due to TEAEs (defined as TEAEs with an action taken with study medication of “drug permanently withdrawn”)
 - Temporary withdrawal of IMP due to TEAEs (defined as TEAEs with an action taken with study medication of “drug temporarily interrupted”)
 - Treatment-related TEAEs
 - Severe TEAEs

All Deaths (AEs leading to death). Note: Above TEAEs will be summarized to capture the overall and by MedDRA Primary SOC (PSOC), Higher level term (HLT) and PT. Additionally, the frequency of TEAEs will be summarized by MedDRA PSOC and PT.

- The number, percentage of participants and frequency of the following TEAEs will be summarized by SOC, HLT and PT for:
 - Incidence of any TEAEs
 - Incidence of Serious TEAEs
 - Incidence of Permanent withdrawal of IMP due to TEAEs
 - Incidence of Any TEAEs by Maximum Intensity (mild, moderate and severe) Incidence of Any TEAEs by Relationship
 - Incidence of Any TEAEs by Event Outcome
 - Incidence of any TEAE's per 100 Patient years.

AESIs are the cases of potential Hy's Law (see [Section 6.1.9](#)).

AESMs or AESIs will be identified based on the assessment by the Investigator as recorded in the CRF. An AE will be counted as an AESMs or AESIs if there is a 'yes' response to the question "Adverse Event of Special Interest or Event of Special Monitoring?" and not otherwise. These flags will be included in the listings.

When applicable, adverse event summaries will be ordered by alphabetical SOC, alphabetical HLT within SOC and decreasing frequency of PT in the rozanolixizumab total column for tables.

Listings of all AEs, permanent withdrawal of IMP due to AEs, participant discontinuation from study due to AEs, and AEs leading to death will be presented by treatment group.

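### Appendix 3 and Table 8-1 leave open whether serious symptoms of the disease are SAEs, and the SAP's all-deaths row can miss a death from disease progression

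*Protocol*

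**What the plan says.** **Protocol Appendix 3 (10.3).** The list of events that are not AEs includes "expected progression, signs, or symptoms of the disease/disorder being studied, unless more severe than expected" for the participant's condition. The SAE definition then adds that a non-AE cannot be an SAE "even if serious conditions are met (eg, hospitalization for signs/symptoms of the disease under study, death due to progression of disease").

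Other parts of the same appendix bring disease events back in:
- Worsening of a chronic or intermittent pre-existing condition, in frequency or intensity, is an AE.
- For treatment failure, "signs, symptoms, and/or clinical sequelae resulting from lack of efficacy will be reported as AE or SAE if they fulfil the definition".
- Convulsions without hospital admission are an example under important medical events.

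**Protocol 8.3.8 and Table 8-1.** The section introduces "Serious AEs anticipated to occur in the population studied in this protocol at some frequency that is independent of drug exposure". The nervous-system and psychiatric rows of the table include convulsion, cluster seizures, memory impairment, cognitive disorder and confusional state. A third row covers falls, fractures and injuries. On reporting: "This list does not change the investigator's obligation to report all SAEs (including Anticipated SAEs"), with a pointer back to 8.3.1 and Appendix 3.

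**SAP 5.6.2.2.** The AE overview has a row for "All Deaths (AEs leading to death"). The corresponding listing is also of AEs that led to death. Section 5.6 has no death output that is independent of AE status.

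**The concern.** There are two linked problems.

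The first is classification. Seizures, memory loss and confusion are the main features of LGI1 encephalitis. They are also what one would see if treatment failed or did harm. If two investigators can each follow the protocol and classify the same hospitalized seizure cluster differently, the SAE table and TEAE incidence (a secondary endpoint) depend partly on which passage was applied.

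The second is the death count. A row labelled as covering all deaths should not depend on whether a death was entered as an AE, least of all when the protocol names a type of death that may not be one.

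**Working it through.** The plan gives no figure to reproduce, so the check is a comparison of texts, followed by arithmetic for scale.

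**Step 1. Trace one event: a participant admitted with a seizure cluster.**

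| Provision | Result |
|---|---|
| Appendix 3, not-an-AE list, if judged expected | Not an AE |
| Appendix 3, SAE definition | Not an AE, so not an SAE despite admission |
| Appendix 3, not-an-AE list, if judged worse than expected | AE, and serious because of admission |
| Appendix 3, worsening of a pre-existing condition | AE if frequency or intensity rose |
| Appendix 3, important medical events | Convulsions usually serious even without admission |
| 8.3.8 and Table 8-1 | Anticipated SAE, to be reported |

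The outcome depends on the word expected, for which no threshold is given. Table 8-1 describes events that occur in this population independently of the drug, which is close to calling them expected. If expected symptoms can never be AEs, the symptom entries in Table 8-1 can hold only events worse than expected, and the table states no such restriction.

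**Step 2. Trace a death from disease progression that the investigator classes as a non-AE.**

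| Output | Would it show the death? |
|---|---|
| SAP 5.6.2.2 overview row for deaths | No, AE-based |
| SAP 5.6.2.2 listing of fatal AEs | No, AE-based |
| SAP 5.2 discontinuation due to AEs, fatal categories | No, AE-based |
| SAP 5.2 primary reason for study termination | Possibly |
| SAP 5.4.2 mRS listing (6 = dead) | Only if a score of 6 was recorded; SAP 6.1.7.1.1 allows no imputation |
| SAP 5.7.1.4 hospitalization listing | Uses a death date only to fill in a missing discharge date |

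**Step 3. Scale.** SAP section 3 gives 12 participants in total. The split by arm is not given, so 4 to 8 per arm is an assumption.
- Overall: 1/12 = 8.3% (exact 95% CI 0.2% to 38.5%) would be shown as 0/12 = 0% (exact upper limit 26.5%).
- One arm: 1/8 = 12.5% to 1/4 = 25.0%; with 6 per arm, 1/6 = 16.7%.
- At the planned size: 68/2 = 34 per arm, and 1/34 = 2.9%.

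**The case against.** The strongest reply is that the passages can be read together. Section 8.3.8 defers to Appendix 3 for what an SAE is, so a Table 8-1 term counts only when it meets that definition. Appendix 3 is conditional, and its provisions on worse-than-expected events, worsening of an existing condition, sequelae of treatment failure and convulsions give most serious seizure events a route to SAE status. This stands in part. It narrows the problem to serious symptoms judged expected, but it does not remove it, because Table 8-1 states no such condition and no threshold is supplied.

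Three stronger readings are tempting, and the documents do not support them:
- A reader might infer that 8.3.8 orders the reporting of the very deaths and hospitalizations that Appendix 3 excludes. It does not: Table 8-1 names symptoms and injuries, and neither death nor hospitalization. The death gap comes from Appendix 3 combined with SAP 5.6.2.2.
- A reader might infer that such events disappear from the trial. They are missing from AE-based outputs. Disposition and mRS may still show a death, and disease-related hospitalization is collected under Protocol 8.10 and listed under SAP 5.7.1.4 where available. None of these is a safety count of deaths.
- A reader might infer that the monitoring committee's death count is wrong. Its data requirements are in a separate charter, and nothing shows that it uses this SAP row.

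It is also fair to say that recruitment was suspended on 29 November 2023, no hypothesis testing is planned, and all AEs are listed. A protocol clarification now may change little of what sites report. The SAP correction is unaffected by this.

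**Conclusion.** The point holds in two parts.

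1. Appendix 3 and 8.3.8/Table 8-1 do not give one answer on whether a serious disease symptom judged expected is reportable. The documents do not settle which rule is intended. The effect depends on investigators' judgement and cannot be sized from the plan.
2. Applied as written, Appendix 3 and SAP 5.6.2.2 together allow a total of all deaths that leaves out a progression death. One such death is 8.3% of the 12 participants, shown as 0%, or 12.5% to 25% of an arm if arms hold 4 to 8.

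The second part assumes that a death occurs and is classed as a non-AE. The documents report no such death, so the figures only illustrate scale. The SAP row should still be corrected before reporting, because its label claims more than its definition delivers.

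**What to change.** - **SAP 5.6.2.2:** replace the AE-restricted row with deaths from any cause, by treatment group, whatever their AE status. Add a matching by-participant listing. Take deaths from every source (AE outcome, study termination page, mRS 6) and reconcile these before unblinding.
- **SAP 5.6.2.2:** show serious disease-related events as a separate row, so that readers can see them with and apart from other SAEs.
- **Protocol Appendix 3, 8.3.8 and Table 8-1:** reconcile the passages under one stated rule for serious symptoms of the disease, including what counts as expected. If the change comes too late to alter site reporting, record the rule and apply it uniformly at blinded data review.

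The SAP changes cost two table rows and one listing, from data the plan already collects. The protocol change is a clarification and may mean somewhat more SAE reporting, depending on the rule chosen.

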#### **A SAE is defined as any untoward medical occurrence that, at any dose:**

##### **a. Results in death**

##### **b. Is life-threatening**

The term ‘life-threatening’ in the definition of ‘serious’ refers to an event in which the participant was at risk of death at the time of the event. It does not refer to an event, which hypothetically might have caused death, if it were more severe.

**c. Requires inpatient hospitalization or prolongation of existing hospitalization**

In general, hospitalization signifies that the participant has been detained (usually involving at least an overnight stay) at the hospital or emergency ward for observation and/or treatment that would not have been appropriate in the physician's office or outpatient setting. Complications that occur during hospitalization are AEs. If a complication prolongs hospitalization or fulfills any other serious criteria, the event is serious. When in doubt as to whether "hospitalization" occurred or was necessary, the AE should be considered serious.

Hospitalization for elective treatment of a pre-existing condition that did not worsen from baseline is not considered an AE.

**d. Results in persistent disability/incapacity**

- The term disability means a substantial disruption of a person's ability to conduct normal life functions.
- This definition is not intended to include experiences of relatively minor medical significance such as uncomplicated headache, nausea, vomiting, diarrhea, influenza, and accidental trauma (eg, sprained ankle) which may interfere with or prevent everyday life functions but do not constitute a substantial disruption.

**e. Is a congenital anomaly/birth defect**

**f. Important medical events:**

- Medical or scientific judgment should be exercised in deciding whether SAE reporting is appropriate in other situations such as important medical events that may not be immediately life-threatening or result in death or hospitalization but may jeopardize the participant or may require medical or surgical intervention to prevent one of the other outcomes listed in the above definition. These events should usually be considered serious.
- Examples of such events include, but are not limited to, potential Hy's law, invasive or malignant cancers, intensive treatment in an emergency room or at home for allergic bronchospasm, blood dyscrasias or convulsions that do not result in hospitalization, or development of drug dependency or drug abuse.

